### **Validation of Hyfe's technical performance**

A subgroup of participants and/or a group recruited outside the clinical setting will provide consent to participate in this sub-study by marking the sub-study box in the consent form.

Participants will remain for approximately 30 minutes in a quiet room. A smartphone connected to a lapel microphone will be placed at approximately 50 cm from the participant's mouth, another smartphone of the same model, not connected to an external microphone will be placed next to the first one. Each participant will also wear a lapel microphone connected to an audio recorder.

Participants will be instructed via a computer monitor to generate a series of voluntary sounds including but not limited to: reading a text, coughing, counting, sneezing and similar common sounds. There will be silent pauses between the elicited sounds. All sounds throughout this period will be recorded. Any accidental conversation will be deleted. The final audio will be stored in a database, coded with the participant's ID, sex, and age.

The cough counts registered by the two smartphones will be compared to the consensus evaluation of two medically trained researchers, who will be instructed to determine whether individual sounds were coughs or not.

Finally, the experiment will be repeated, playing back the records obtained from participants using a desktop speaker located at 50 cm of the two smartphones, to compare the application's performance detecting live vs recorded coughs. Audio will be played at decibels matching the average intensity of human coughs (Doherty et al, 1997).

A second sub-group of at least 24 participants will be instructed to use Hyfe continuously for a period between 6 and 24 hours, while they record themselves using a MP3 recorder connected to a lapel microphone. For this, participants will be provided with a smartphone exclusively destined to run Hyfe Cough Tracker, while simultaneously wearing the Hyfe Air wearable system. MP3 records will be processed and manually reviewed by two specially trained healthcare providers to count the number of coughs recorded. This data will be used to evaluate the performance of both devices compared to human listeners in a real-life scenario.

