### **7.2. Efficacy variables**

For the primary objective 1, efficacy will be measured by determining Hyfe's capacity to predict a diagnosis, or reflect clinical evolution of patients, based on cough signatures. For this, the acoustic characteristics of coughs (mean frequency, volume, amplitude) registered from participants with an etiologic diagnosis, will be described, to identify patterns associated to specific conditions. Additionally, the Area Under the Curve, sensitivity, and specificity of the AI system will be retrospectively evaluated with the annotated cough registries.

For the secondary objective 1, the efficacy variable will be the daily score in the online VAS, and the coughs per recorded hour.

For the secondary objective 2, there is no clear efficacy variable. We will retrospectively include anonymous coughs registered in patients with an etiologic diagnosis and annotated with data in online datasets from where they can be used to train this and similar AI systems in the future.

For the secondary objectives 3 and 4, efficacy variables will include the calculated sensitivity, specificity, positive predictive value (PPV), and negative predictive value (NPV) of Hyfe, compared to two trained human observers.

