## 9. STATISTICS

### ***9.1. Description of the statistical methods to be used, including the schedule of all the planned intermediate analyses***

For completion of the primary objective

To assess the accuracy of the cough surveillance system to detect cough patterns associated to specific diseases, we will use participants in which an etiologic diagnose is reached before completion of the study. We will search for digital footprints of singular detected cough events, and/or the pattern of cough in time for participants with a given diagnosis.

These records will be used to train a previously developed convolutional neural network to perform respiratory disease cough classification. We will initially use a random split-sample approach (70% derivation & 30% validation) to assess the performance of the newly generated cough classification tool (sensitivity, specificity, positive and negative predictive values, AUC). Performance will then be validated by retrospectively analyzing these participants' coughs with the newly trained AI-network.

The cough classification tool will be supplemented with patient-specific information to assess the incremental value of cough-based multi-variable prediction.

For secondary objective 1

The daily VAS score of participants will be compared to the cough frequency registered by the cough surveillance system. These data will be used to fit a linear regression model to compare self-reported VAS scores to daily cough frequency and calculate a correlation coefficient ( $r$ ). The

average weekly VAS score and cough frequency on week 1, will be compared to that at study withdrawal using a paired t-test, and represented using before-after plots. P values below 0.05 will be considered significant. A similar approach will be used to compare results of the LCQ at the beginning vs the end of the study. Before-after plots will be constructed to represent these differences. This approach is also expected to provide information on the system's capacity to reflect clinical evolution of participants (Primary objective).

For completion of secondary objective 2

Cough registries of participants with an etiologic diagnosis of respiratory disease will be included in annotated datasets. There are no specific statistical analysis required for completion of this objective.

For completion of secondary objectives 3 and 4

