The validation parameters for the application will be calculated in the following way: Sensitivity = True positives (TP)/True positives (TP) + False negatives (FN), Specificity = True negatives (TN)/True negatives (TN)+ False positives (FP). PPV= TP/TP+FP, NPV= TN/TN+FN.

Any sound identified as a cough by both human observers will be considered a positive result for cough. TP will be defined as those sounds identified as a cough by Hyfe, and both human observers. Similarly, a sound identified as non-cough by both observers will be considered a negative. TN will be defined as those sounds not recorded as coughs by neither Hyfe, nor any human observer. Sounds identified as coughs by Hyfe, but not by both human observers will be considered FP, and those identified as non-cough by Hyfe, but not by both human observers will be classified as FN. Sounds for which no consensus is reached by both human observers will be excluded from the analysis. Time stamps from each individual sound will be used to identify them, and determine which ones were not picked up by Hyfe's detection algorithm.

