## **9.2. Sample size calculations**

### *Primary objective*

For the primary objective, sample size calculations are complicated due to the variability of cough frequency between different patients with different conditions. To evaluate the system's capacity to detect and classify coughs based on their etiology, we will create and prospectively

increase a split-sample (derivation / validation) dataset and test performance until it plateaus (see data analysis). Based on previous digital cough diagnostic studies performed by the co-investigators, we anticipate needing 15,500 individual cough data points and 200 cough time series by groups for every individual diagnosis. This number of coughs might be rapidly reached by participants diagnosed with a cause of chronic cough but will likely take substantial time for other acute conditions. Thus, the suggested duration of 5 years.

To evaluate the capacity of the system to reflect changes in cough frequency associated to clinical evolution, sample size calculations are more straightforward and detailed below.

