#### Secondary objective 3:

We aim to determine the sensitivity and specificity of Hyfe to detect and classify coughs appropriately. For this objective, all coughs will be voluntary, so the cough prevalence of coughs in our sample will be 100%. Including a minimum of 24 patients with 12 voluntary coughs each (288 coughs in total) will be required to achieve a power of 90% at 5% significance level to detect a difference of 5% in the value of sensitivity from 95% in the human observer to 90% by Hyfe. This minimum sample size is also sufficient to detect with 70% power a difference in specificity of 10% from 90% in the human observer to 80% in Hyfe at 5% significance. (Bujang and Adnan, 2016).

#### Secondary objective 4

Given the similarity with secondary objective 3, the same sample size calculation method was used. Twenty-four participants (12 males and 12 females, preferentially from different age groups) will be recruited for this exploratory analysis.

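### PPV and NPV from the scripted session (objective 3) and from the diagnosed-only dataset (primary objective) depend on the sample mix as well as on the tool, so they do not estimate predictive values in real use

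*Combined protocol and SAP*

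**What the plan says.** **Cough detection (objectives 3 and 4).** Section 7.2 states that "efficacy variables will include the calculated sensitivity, specificity, positive predictive value (PPV), and negative predictive value (NPV) of Hyfe", with two trained human observers as the reference. Section 9.1 gives the formulas as "PPV= TP/TP+FP, NPV= TN/TN+FN" (brackets implied), which are raw cell counts.

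The objective 3 data come from a session of about 30 minutes in a quiet room (section 4, Validation of Hyfe's technical performance): "Participants will be instructed via a computer monitor to generate a series of voluntary sounds including but not limited to: reading a text, coughing, counting," and so on, with sneezing also listed. The number of each sound is not given. Section 9.2 fixes the coughs at 24 participants × 12 = 288 and gives no count of other sounds. Objective 4 instead uses continuous recordings of 6 to 24 hours in a real-life setting.

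**Diagnosis classifier (primary objective).** Section 9.1 assesses the tool in a 70/30 split by "sensitivity, specificity, positive and negative predictive values, AUC". The data come only from participants in whom an etiologic diagnosis is reached. Section 9.2 anticipates a need for 15,500 coughs and "200 cough time series by groups for every individual diagnosis". For the same objective, section 7.2 says only that "the Area Under the Curve, sensitivity, and specificity of the AI system will be retrospectively evaluated with the annotated cough registries"; PPV and NPV are absent there.

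No section gives a cough to non-cough ratio, a target prevalence, a prevalence adjustment, or a limit on how the predictive values are to be read.

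**The concern.** Readers take PPV as the chance that a positive result is right, and NPV as the chance that a negative one is. Both change with how common the target is in the sample. In the scripted session that frequency is a choice made when the script is written. In the classifier dataset it reflects who received a diagnosis and how accrual ran, and undiagnosed cough patients are absent.

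The primary objective in section 3 concerns screening, diagnosis and management in clinical practice. Raw predictive values from either sample could be carried into that setting as if they applied there. The same tool could show very different values under two scripts, and the plan as it stands would not let a reader see that.

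**Working it through.** The plan states no PPV or NPV, so there is no figure to reproduce. The check asks how far the mix alone can move them.

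**Formulas.** With sensitivity Se, specificity Sp and share p of true positives in the sample:

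- PPV = Se·p / [Se·p + (1 − Sp)(1 − p)]
- NPV = Sp(1 − p) / [Sp(1 − p) + (1 − Se)p]

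**Objective 3 inputs.** Se = 0.9634 and Sp = 0.9654 are the preliminary figures in section 6. The share p is an assumption, because the script's mix is not stated.

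| Cough share p | PPV | NPV |
|---|---|---|
| 10% | 0.756 | 0.996 |
| 50% | 0.965 | 0.963 |
| 90% | 0.996 | 0.746 |

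The same result in counts, with the planned 288 coughs, so TP = 0.9634 × 288 = 277.5 and FN = 0.0366 × 288 = 10.5:

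- *10% share:* 288 × 9 = 2,592 other sounds. FP = 0.0346 × 2,592 = 89.7 and TN = 2,502.3. PPV = 277.5/367.1 = 0.756; NPV = 2,502.3/2,512.9 = 0.996.
- *90% share:* 288/9 = 32 other sounds. FP = 0.0346 × 32 = 1.1 and TN = 30.9. PPV = 277.5/278.6 = 0.996; NPV = 30.9/41.4 = 0.746.

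As non-coughs per cough (R), PPV = Se/[Se + (1 − Sp)R]:

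- R = 1: 0.9634/0.9980 = 96.5%
- R = 10: 0.9634/1.3094 = 73.6%
- R = 50: 0.9634/2.6934 = 35.8%

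**Does the tool still matter?** Yes. With the mix held at 50%:

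| Se / Sp (assumed) | PPV | NPV |
|---|---|---|
| 0.90 / 0.80 | 0.818 | 0.889 |
| 0.95 / 0.90 | 0.905 | 0.947 |
| 0.99 / 0.99 | 0.990 | 0.990 |

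**Classifier.** The documents give no accuracy or prevalence for any diagnosis, so Se = 0.80, Sp = 0.90 and the shares below are all assumptions.

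| Share with the diagnosis | PPV | NPV |
|---|---|---|
| 25% | 0.200/0.275 = 0.727 | 0.675/0.725 = 0.931 |
| 5% | 0.040/0.135 = 0.296 | 0.855/0.865 = 0.988 |
| 1% | 0.008/0.107 = 0.075 | 0.891/0.893 = 0.998 |

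Leaving out undiagnosed patients moves the share directly. The share among all enrolled equals the share among the diagnosed times the fraction diagnosed, if the undiagnosed do not have the condition. For example, 25% of the diagnosed becomes 5% of the enrolled when one in five is diagnosed (0.25 × 0.2 = 0.05). That fraction is also assumed.

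**The case against.** Several points on the other side stand.

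- **Correct for the sample.** TP/(TP + FP) is a valid description of the sounds analysed, and the limit is on carrying it elsewhere. Section 3 names only sensitivity and specificity for objectives 3 and 4. No power statement or decision rule rests on a predictive value.
- **Real-life PPV is already planned.** The sentence in section 7.2 also covers objective 4, where the mix is not scripted.
- **The inputs are illustrative.** The section 6 figures come from explosive sounds that the app had already detected, and the shares are assumed.

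Four stronger readings are tempting, and the documents do not support them.

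- *PPV will be 100% by construction.* The objective 3 sample-size text says "all coughs will be voluntary, so the cough prevalence of coughs in our sample will be 100" per cent, and a reader might infer PPV = 1 and NPV = 0. But section 4 scripts non-cough sounds and section 9.1 defines true negatives and false positives for them. That sentence is a sample-size premise that conflicts with the design, and it does not predict the reported result.
- *The mix alone sets the values.* At a fixed 50% mix, PPV still runs from 0.818 to 0.990 as the tool improves.
- *A quota fixes class prevalence.* Section 9.2 gives an anticipated requirement per diagnosis. No section caps or balances groups, and all participants with an etiologic diagnosis are to enter the annotated datasets. The mix is shaped by selection and accrual targets and is not fixed.
- *Both values will look too good.* NPV moves the opposite way to PPV. For objective 3 even the direction for PPV cannot be known, because the script's ratio is not given.

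Labelling the values with their sample mix would help. It would still leave, among the objective 3 efficacy variables, two figures that another script would change.

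**Conclusion.** The point holds in a limited form. The planned PPV and NPV for objective 3 and for the classifier depend jointly on the tool and on a mix that arises from the script or from selection on diagnosis. They therefore do not estimate predictive values in real use, and the plan neither adjusts nor limits them.

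For objective 3, the mix alone can move PPV by 0.24 (0.756 to 0.996) and NPV by 0.25 (0.996 to 0.746). This rests on the section 6 accuracy figures and on assumed cough shares of 10% to 90%. The classifier figures are illustrations only. If real use has a lower share of coughs or of the diagnosis than the sample, the raw PPV is too high and the raw NPV too low.

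Sensitivity, specificity, AUC and the objective 4 PPV are not called into question by this point. It is a low-cost correction to reported efficacy figures and does not challenge the design.

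**What to change.** In sections 7.2 and 9.1:

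1. **Objective 3:** report sensitivity and specificity only.
2. **Objective 4:** keep the planned real-life PPV as the predictive value for cough detection, and give the cough share in those recordings beside it.
3. **Classifier:** replace raw split-sample PPV and NPV with values recalculated by the formulas above. Use the diagnosis mix among all enrolled cough patients, with the undiagnosed in the denominator, and also a stated prevalence range. Say that this assumes sensitivity and specificity carry over to patients without a diagnosis.
4. **Consistency:** make sections 7.2 and 9.1 list the same measures for the primary objective.

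The cost is a few lines of text and one recalculation, with no new data. The reported PPV may be less favourable.

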### **7.3. Schedule for evaluation, recording and analysis of the efficacy parameter**

Participant recruitment is set to start in Q3 2021. Cough registries of patients with an etiologic diagnosis will start to be included in the annotated datasets as soon as the diagnosis is reached.

## 8. SAFETY APPRAISAL

This study is considered safe. There are no anticipated risks or benefits from participants taking part in this study. All participants can withdraw from the study at any point, prior notification to researchers.

Privacy concerns will be addressed by clarifying that no sound beyond 0.5 seconds of every cough is ever stored. All measures taken to protect patient's privacy and confidentiality are detailed in the "confidentiality" section.

## 9. STATISTICS

### ***9.1. Description of the statistical methods to be used, including the schedule of all the planned intermediate analyses***

For completion of the primary objective

To assess the accuracy of the cough surveillance system to detect cough patterns associated to specific diseases, we will use participants in which an etiologic diagnose is reached before completion of the study. We will search for digital footprints of singular detected cough events, and/or the pattern of cough in time for participants with a given diagnosis.

These records will be used to train a previously developed convolutional neural network to perform respiratory disease cough classification. We will initially use a random split-sample approach (70% derivation & 30% validation) to assess the performance of the newly generated cough classification tool (sensitivity, specificity, positive and negative predictive values, AUC). Performance will then be validated by retrospectively analyzing these participants' coughs with the newly trained AI-network.

The cough classification tool will be supplemented with patient-specific information to assess the incremental value of cough-based multi-variable prediction.

For secondary objective 1

The daily VAS score of participants will be compared to the cough frequency registered by the cough surveillance system. These data will be used to fit a linear regression model to compare self-reported VAS scores to daily cough frequency and calculate a correlation coefficient ( $r$ ). The

average weekly VAS score and cough frequency on week 1, will be compared to that at study withdrawal using a paired t-test, and represented using before-after plots. P values below 0.05 will be considered significant. A similar approach will be used to compare results of the LCQ at the beginning vs the end of the study. Before-after plots will be constructed to represent these differences. This approach is also expected to provide information on the system's capacity to reflect clinical evolution of participants (Primary objective).

For completion of secondary objective 2

Cough registries of participants with an etiologic diagnosis of respiratory disease will be included in annotated datasets. There are no specific statistical analysis required for completion of this objective.

For completion of secondary objectives 3 and 4

The validation parameters for the application will be calculated in the following way: Sensitivity = True positives (TP)/True positives (TP) + False negatives (FN), Specificity = True negatives (TN)/True negatives (TN)+ False positives (FP). PPV= TP/TP+FP, NPV= TN/TN+FN.

Any sound identified as a cough by both human observers will be considered a positive result for cough. TP will be defined as those sounds identified as a cough by Hyfe, and both human observers. Similarly, a sound identified as non-cough by both observers will be considered a negative. TN will be defined as those sounds not recorded as coughs by neither Hyfe, nor any human observer. Sounds identified as coughs by Hyfe, but not by both human observers will be considered FP, and those identified as non-cough by Hyfe, but not by both human observers will be classified as FN. Sounds for which no consensus is reached by both human observers will be excluded from the analysis. Time stamps from each individual sound will be used to identify them, and determine which ones were not picked up by Hyfe's detection algorithm.

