## **2.2. Diseases under study**

For the current study we will focus on patients who present to the pneumonology, check-ups and infectious diseases outpatient clinic at the Clínica Universidad de Navarra with cough. This includes patients with cough of unknown origin and those with a previously diagnosed respiratory disease. As a symptom, cough: (i) represents an important reason for consultation at the clinic, (ii) represents a diagnostic challenge, and (iii) is an indicator of the efficacy of specific treatments for underlying respiratory conditions.

Examples of these conditions include, but are not limited to:

- **Chronic cough:** Typically considered to be any cough that lasts for 8 weeks or longer. This condition is thought to affect around 10% of the world adult population and can be caused by a myriad of different conditions, including: allergies, sinus infection, asthma, chronic obstructive pulmonary disease (COPD), cancer, gastroesophageal reflux disease (GERD), among others. (Song et al, 2016).

Its diagnostic process is typically lengthy, and largely based on empiric observations of response to different treatment schemes, which is in turn dependent on subjective reports from patients. Designing a method to objectively monitor this process will likely speed up diagnosis and lead to improved clinical outcomes and reduced costs in the healthcare sector.

- **Tuberculosis:** *Mycobacterium tuberculosis* is the leading infectious cause of death in the world, with most cases occurring in low-income countries. Global prevalence is unknown, but 25-47%

of the total population of India, China, the Philippines, and Pakistan (the five countries with the highest burden) are estimated to be infected (Ragonnet, Trauer, Geard, 2019). Chronic cough is a symptom of pulmonary tuberculosis, and a major driver for transmission of the disease (Turner, 2019).

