### **Generation of annotated cough datasets**

Participants with an etiologic diagnosis at the time of enrollment, or in which it is reached before the end of the monitoring period, will be retrospectively included in disease-annotated datasets, to assess differences in the acoustic patterns of specific diseases with the neural network created by Hyfe.

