### **6.1. Drugs or treatments that are permitted (including rescue medication) and not permitted before and/or during the trial**

No medications or specific treatments will be prescribed to participants as part of this study. Participants shall continue with any pre-established treatment, or those newly prescribed by their treating doctor during the study period. All treatment prescribed will be recorded in the patients file and study database.

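### Section 9.1 sets no recording window for the disease classifier, so its diagnostic accuracy can partly reflect treatment or treatment response instead of disease

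*Combined protocol and SAP*

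**What the plan says.** **Predictor.** Section 9.1 builds the disease classifier on individual coughs, on the course of cough over time, or on both: "We will search for digital footprints of singular detected cough events, and/or the pattern of cough in time for participants with a given diagnosis". Section 9.2 anticipates 200 cough time series per diagnosis, so the time pattern is a planned input.

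**Who enters.** Section 9.1: "we will use participants in which an etiologic diagnose is reached before completion of the study". The section on generating annotated datasets takes in "Participants with an etiologic diagnosis at the time of enrollment, or in which it is reached before the end of the monitoring period". Section 7.3 adds: "Cough registries of patients with an etiologic diagnosis will start to be included in the annotated datasets as soon as the diagnosis is reached". None of these says which part of a participant's recording is used.

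**Treatment during recording.** Section 6.1: "Participants shall continue with any pre-established treatment, or those newly prescribed by their treating doctor during the study period". Section 4.1 also foresees monitoring of participants who are receiving treatment.

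**How labels arise.** On chronic cough, section 2.2 says: "Its diagnostic process is typically lengthy, and largely based on empiric observations of response to different treatment schemes". Section 7.1.1 has the treating physician enter the diagnosis on a questionnaire. No reference standard is defined for any disease.

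**Validation.** Section 9.1 uses a random 70% derivation and 30% validation split, then re-analyses the same participants' coughs with the trained network.

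**The concern.** Section 3 asks whether acoustic cough patterns can help reach an etiologic diagnosis in chronic cough. The patient for whom that matters has no diagnosis yet and has not yet shown a response to the treatment that will settle it. The data allowed into the classifier need not look like that, in two distinct ways.

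(a) *Shared information between label and predictor.* If a participant is diagnosed during monitoring because cough improved on a treatment, the recorded time pattern contains the improvement that informed the label.

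(b) *Confounding by treatment.* A participant diagnosed before enrolment contributes only post-diagnosis cough, often on treatment. The network can separate diagnoses by what current treatment does to cough.

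In either case sensitivity, specificity and AUC could look good without showing that cough helps anyone reach a diagnosis.

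**Working it through.** The plan gives no target accuracy, power or other figure on this point, so there is nothing of its own to reproduce. The check has two parts.

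**1. Which recordings can enter, by time of diagnosis.**

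| Diagnosis made | Cough available | Exposure |
|---|---|---|
| At or before enrolment | All after diagnosis | (b); the response that set the label came before recording |
| During monitoring, from treatment response | Can span the treatment trial | (a) for time pattern; (b) for on-treatment cough |
| During monitoring, from an independent test | Can span diagnosis and treatment start | (b) |

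No section excludes any row, or any part of a recording within a row. A single snippet of about 0.5 seconds cannot contain a before/after change, so single-cough acoustics are exposed mainly to (b).

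**2. How large (a) could be.** All inputs here are assumptions, not figures from the documents. Pre-treatment cough carries no information, so the true AUC is 0.50. The true change in log cough rate on treatment is D, normal with mean -0.5 and SD 0.8. The patient reports R = D + noise, with noise SD s = 0.3, 0.6 or 1.0. A response-based label is given when the reported fall is at least 50%, that is R < ln 0.5 = -0.693. The predictor is D.

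*Two response-defined diagnoses under the same rule.* Both groups are selected on R < -0.693, so D has the same distribution in each and the AUC is 0.50 for every s.

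*Response-defined against test-defined, same underlying change.* The test-defined group is unselected on R. A share p of it would have met the response rule and 1 - p would not, with

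p = Φ((-0.693 + 0.5)/√(0.64 + s²)).

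With A the AUC of D between those who meet the rule and those who do not (from simulation, used only as an intermediate quantity), the AUC is 0.5p + (1 - p)A.

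| s | p | A | 0.5p + (1 - p)A |
|---|---|---|---|
| 0.3 | 0.411 | 0.962 | 0.205 + 0.567 = 0.77 |
| 0.6 | 0.423 | 0.883 | 0.212 + 0.509 = 0.72 |
| 1.0 | 0.440 | 0.789 | 0.220 + 0.442 = 0.66 |

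Direct simulation agrees.

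*Test-defined disease that improves more on treatment* (assumed mean change -1.0): simulated AUC 0.58, 0.53 and 0.48. The artefact shrinks and can change direction.

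*Only a share w of the first diagnosis labelled by response*, the rest by a test with the same change: AUC = 0.5 + w(AUC - 0.5). For w = 0.5 this gives 0.64, 0.61 and 0.58; for w = 0.25 it gives 0.57, 0.56 and 0.54.

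*Does the split help?* A random 30% of the same participants has the same joint distribution of label and predictor, so it has the same expected AUC. In simulation, hold-out and full-sample values agree within 0.005. A feature taken before treatment stays at 0.50.

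**The case against.** Several counter-arguments have force.

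- *A reader might compare responders with non-responders and infer a spurious AUC of 0.79 to 0.96* (column A above). The documents do not support that contrast. Section 9.1 analyses only participants who reach a diagnosis and separates one disease from another, so someone who does not respond to a treatment is not the comparator for the diagnosis it would have established.
- *A reader might call the whole problem incorporation bias.* That is not shown. Section 2.2 says the response is judged from patients' subjective reports, not from the app's counts. For diagnoses made before enrolment, the problem is confounding by treatment.
- *Section 2.2 is background.* It describes typical practice in chronic cough and is not a study reference standard. Section 4.1 also foresees a route through diagnostic procedures, and tuberculosis, NTM and asthma are not described as diagnosed by response. The share of response-based labels is therefore unknown. Still, it is the plan's only account of how chronic-cough labels arise, and nothing excludes them.
- *Section 7.2 stresses acoustic characteristics of coughs.* This narrows (a) to time-pattern features but leaves (b).
- *The trial's title concerns known respiratory disease, and the primary objective includes management.* On-treatment recording is intended and valid there. Only the diagnostic claim is affected.

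**Conclusion.** The concern holds in limited form. As written, section 9.1 allows the diagnostic accuracy estimate to be influenced by treatment response (time-pattern features, response-based diagnoses made during monitoring) and by current treatment (any feature, participants already diagnosed or treated). The planned split cannot show either.

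The size cannot be determined from the documents. It depends on the share of response-based labels and on which diagnoses are compared. Under the assumed inputs, the artefact in the time-pattern AUC runs from none (0.50) for two response-defined diagnoses to about 0.66 to 0.77 for a response-defined against a test-defined diagnosis with the same underlying change. It is smaller if only some labels rest on response or if the test-defined disease improves more. These values illustrate mechanism (a) only. The size of (b) was not estimated.

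**What to change.** In section 9.1:

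1. Base the claim that cough helps reach a diagnosis on validation participants with no etiologic diagnosis at enrolment. Use only cough recorded before the diagnosis date and before the start of the treatment whose response established the diagnosis.
2. Report accuracy in known or treated disease separately and under that name. Keep those recordings for training, the annotated dataset and the management objective.
3. Show time-pattern results without participants diagnosed by treatment response.
4. Add the date and basis of diagnosis to the existing medical questionnaire.

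The rest of the data is already collected. On treatment, section 6.1 says: "All treatment prescribed will be recorded in the patients file and study database". Section 6 has coughs matched with time. Clinical management does not change.

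The cost is SAP wording, two questionnaire items, and a smaller validation subset with wider intervals. Because many participants may arrive already diagnosed or treated, some diagnoses may have too few time series, set against the 200 anticipated in section 9.2. In that case the diagnostic claim should be limited to what the subset supports.
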